Non-operative management of splenic and hepatic injuries has become one of the standards of care in the management of hemodynamically stable patients. Institutional variance exists in management of these injuries regarding serial laboratory values, transfusion thresholds, the utility of interventional radiology/operative management, follow up imaging, and management of delayed findings on this imaging. The delayed complications found both clinically and with follow up imaging vary in the literature from nearly 0% to >15% of cases. There is no clear evidence as to the necessity of repeat imaging or frequency of intervention in blunt splenic and hepatic injuries. Some studies recommend only follow up

imaging for high grade injuries, whereas other studies have found no correlation between grade of injury and complications.

Our group approached this question through a dual institution, retrospective pilot study observing the management of delayed splenic and hepatic complications found on repeat imaging. This study was performed in the adult population and a current study is ongoing in the pediatric population. Imaging was obtained either via the institutions standard protocol (SP) or physician discretion (PD) (lab or vital sign abnormalities, clinical change, etc). There were 235 splenic injuries with 45% undergoing repeat imaging. 64% of these were due to PD. Complications were found in 47% of SP and 42% of PD patients (p=0.683). Interventions performed for these complications was done for 56% SP v. 21% of PD patients (p=0.027). This pilot study suggested that patients with blunt splenic injuries should undergo repeat imaging for delayed complications and that those who underwent repeat imaging by SP had complications identified sooner (2.4 v 4.4 days) and treated earlier than the PD group.

Of the 365 liver injuries, 33.4% underwent repeat imaging with a majority (59%) of these due to physician discretion. Complications were found in 20% of SP patients and 27% of PD patients (p=0.395). Interventions were performed in 20% SP v. 25% PD patients that had complications (p=1.00). In the liver injury group there was no difference found between complications or interventions performed when assessed by SP or PD; waiting to perform repeat imaging based on PD could prevent unnecessary imaging in blunt liver injuries.

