The time frame for data query will be from IRB approval (2020) until December 31, 2023. The electronic medical record (EMR) may be used in order to identify participants who match study defined demographic criteria.

Primary Outcome: Delayed complications found on repeat imaging

Secondary Outcomes: Timing to repeat imaging/ intervention, interventions performed based on complications found, mortality, length of stay, blood transfusion requirements, VTE prophylaxis, and 30 day readmission variables [readmission within 30 days for spleen and/or liver injury, readmission CT scan, interventions performed].

Variables

List specific variables to be collected & analyzed: Age, sex, time from injury, Injury Severity Score (ISS), Abbreviated Injury Scale (AIS), Trauma and Injury Severity Score (TRISS), mechanism of injury, initial vital signs, anticoagulant use and reversal agents, initial and repeat imaging, grade of organs injured, complications found, details regarding initial and any delayed interventions, blood transfusions, details regarding venous thromboembolism prophylaxis, venous thromboembolism complications, hospital length of stay, intensive care unit length of stay, mortality, and 30 day readmission variables [readmission within 30 days for spleen and/or liver injury, readmission CT scan, interventions performed].

Data Collection and Statistical Analysis

Standardized data will be collected for each patient meeting inclusion criteria (see data collection tool). The de-identified data for each patient will be entered into a secure REDCap database. A total of 5,000 patients (3,500 splenic injuries and 1,500

hepatic injuries) is recommended to identify a significant difference between the non clinical change and clinical change group. Complications found on repeat imaging will be assessed using univariate and multivariate analysis.

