Categorical variables will be compared using Fisher's exact test or Chi-squared test. Continuous variables will be assessed using Student's t-test. For multivariate analysis, a mixed effect multinomial logistic regression will be run with a binary outcome of whether the patient had a delayed complication. Another mixed effect multinomial logistic regression will be run with a binary outcome of whether the patient had an intervention performed. Additional analysis will be completed to determine if there is optimal timing for repeat imaging to identify complications. Data will be reported as adjusted odds ratios with 95% confidence intervals. Statistical significance will be defined by a p<0.05.

Sample Size and Power Estimates

A retrospective pilot study was completed with 235 patients with splenic injuries and 365 hepatic injuries. Of the patients with splenic injuries, 105 underwent repeat imaging, 46 had organ specific complications, and 16 had an intervention performed. Of the patients with hepatic injuries, 122 underwent repeat imaging, 30 had organ specific complications, and 12 had an intervention performed.

Spleen Power Analysis

Combined complication rate for patients who had repeat imaging: 46/105 = 0.44Standard protocol complication rate: 18/38 = 0.47Physician discretion complication rate: 28/67 = 0.42

Complication Rate:	Complication Rate:	Odds Ratio	Sample Size
Standard protocol	Physician discretion		(Total Population)
0.46	0.43	0.89	8,614
0.47	0.42	0.82	3,100
0.48	0.41	0.75	1,582

Liver Power Analysis

Combined complication rate for patients who had repeat imaging: 30/122 = 0.25Standard protocol complication rate: 10/50 = 0.20Physician discretion complication rate: 20/72 = 0.27

Complication Rate: Standard protocol	Complication Rate: Physician discretion	Odds Ratio	Sample Size (Total Population)
0.21	0.26	1.32	2,256
0.20	0.27	1.48	1,150
0.19	0.28	1.66	696

Consent Procedures

This is a retrospective observational study in which data will be retrospectively recorded on patients according to institutional protocols. Data will be input into REDcap database without any patient identifiers. Thus, a waiver of consent is requested.

Confidentiality and Privacy

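### Student's pooled-variance t-test is the only method named for continuous outcomes, although times, stay and transfusion are probably skewed and the groups unequal; a minor weakness, cheaply mended

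*Supplement*

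**What the plan says.** The rule stands in the protocol under Data Collection and Statistical Analysis, with the same wording in both copies in the supplement: "Continuous variables will be assessed using Student's t-test". The threshold follows: "Statistical significance will be defined by a p<0.05". No Welch version, rank test, transformation, time-to-event method or check of distribution is named.

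The secondary outcomes begin "Timing to repeat imaging/ intervention, interventions performed based on complications found, mortality, length of stay, blood transfusion requirements". The data dictionary shows how they are recorded:

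- Times to imaging and intervention are in hours from admission or presentation. Intervention time is entered only if an intervention took place.
- Hospital and ICU stay are in days, with the admission day counted as day 1.
- Transfusion is in units and ml. Patients without transfusion contribute zero.

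The two planned regressions have binary outcomes (delayed complication, intervention), so they do not cover these variables. A further analysis of the best time for repeat imaging is announced without a method. No standard deviation or distribution is given for any continuous variable.

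**The concern.** Student's test pools the two variances and relies on means that are close to normally distributed. Times, stay and transfusion are bounded below and usually have a long right tail. Two separate harms can follow.

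The first is lost power: a few long values inflate the standard error of the mean, most of all in small sets. The second is a wrong error rate: if the groups differ in both size and spread, the pooled standard error is wrong, and more patients do not correct it. Unequal spread is plausible here, because one group includes scheduled scans and the other is scanned when symptoms or signs arise. That is an inference; the documents give no figures on it.

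At stake are the unadjusted group comparisons of timing, stay and transfusion, which would feed into a management guideline.

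**Working it through.** **1. The plan's own figures.** The sample-size tables concern proportions only. For spleen, 0.47 v 0.42, two-sided 5%, 80% power, 1:1:

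n per group = [1.960 × √(2 × 0.445 × 0.555) + 0.8416 × √(0.2491 + 0.2436)]² / 0.05² = (1.3775 + 0.5908)² / 0.0025 ≈ 1,550, total 3,100, as printed.

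The other five rows also reproduce exactly. No calculation is offered for a continuous outcome.

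**2. Projected group sizes.** Pilot, spleen (235 patients): "105 underwent repeat imaging, 46 had organ specific complications, and 16 had an intervention performed". Pilot, liver (365 patients): "122 underwent repeat imaging, 30 had organ specific complications, and 12 had an intervention performed". Scaled to the planned 3,500 and 1,500, with standard protocol (now non-clinical change) first:

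- Spleen, repeat imaging: 38/235 × 3,500 = 566; 67/235 × 3,500 = 998.
- Liver, repeat imaging: 50/365 × 1,500 = 205; 72/365 × 1,500 = 296.
- Spleen, intervention: 0.56 × 18/235 × 3,500 = 150; 0.21 × 28/235 × 3,500 = 88.
- Liver, intervention, from the group percentages: 0.20 × 10 = 2 and 0.25 × 20 = 5, which scale to 8 and 21 (29 in all).
- Liver, intervention, from the count of 12: 12/365 × 1,500 = 49, or 14 v 35 if split 2:5.

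The counts of 12 and 7 may measure different things; both are carried.

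**3. Type I error of the pooled test, equal means.** For log-normal data with equal means, the variance is proportional to v = exp(s²) − 1, where s is the log-SD (assumed). In large samples the true size is 2 × [1 − Φ(1.96 × √(P/T))], with

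- T = v₁/n₁ + v₂/n₂
- P = pooled v × (1/n₁ + 1/n₂)

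At 566 v 998:

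| log-SD (566 v 998) | v₁, v₂ | P/T | Size by formula | Student, simulated |
|---|---|---|---|---|
| 1.0 v 0.8 | 1.718, 0.896 | 0.840 | 7.2% | about 7% |
| 0.8 v 1.0 | 0.896, 1.718 | 1.190 | 3.2% | about 3% |
| 1.2 v 0.6 | 3.221, 0.433 | 0.652 | 11.4% | about 12.6% |
| 0.6 v 1.2 | 0.433, 3.221 | 1.534 | 1.5% | about 2.4% |

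The SD ratio is √(1.718/0.896) = 1.4 in the first pair and √(3.221/0.433) = 2.7 in the second. P/T depends on the ratio of group sizes, not on the total, so the error does not fade as n grows. Remaining skew explains the gap between formula and simulation in the last two rows. Welch's test lay between about 5% and 7% in these settings. With the same shape in both groups, Student's test was at 3.7-5.3% at every size tried.

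**4. Power, same shape in both groups.** Log-normal times with medians 2.4 and 4.4 days. The documents give these as splenic times to identification and do not call them medians; they serve here only as an illustrative ratio of 1.83.

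| Contrast | log-SD | Student | Rank-sum |
|---|---|---|---|
| Liver intervention, 8 v 21 | 0.5 | about 68% | 77% |
| | 0.8-1.2 | about 20% down to 5% | 40% down to 20% |
| Liver intervention, 14 v 35 | 0.5 | about 92% | 94% |
| | 0.8-1.2 | about 43% down to 10% | 62% down to 32% |
| Spleen intervention, 150 v 88 | 1.2 | 79% | 96% |
| Liver imaging, 205 v 296 | 0.8-1.2 | 96-100% | about 100% |
| Spleen imaging, 566 v 998 | 0.8-1.2 | 100% | 100% |

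For spleen intervention the loss is small below log-SD 1.2. Smaller differences lose power even in large sets: at 566 v 998 with a mean ratio of 1.15 and a coefficient of variation of 1.5, Student's test has 44% and rank-sum 68%.

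**5. What the alternatives test.** With equal means and log-SD 1.2 v 0.6 at 566 v 998, rank-sum rejects about 100% of the time, because the medians differ. It answers another question and does not cure the error in step 3. Welch does so at large n, but at 8 v 21, with the smaller group twice as variable, it still runs at 11-15%.

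**The case against.** The strongest reply is that this is a routine wording point about unadjusted secondary comparisons. The primary outcome is binary, and neither the sample size nor the regressions use a t-test. That stands.

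A reader might go further than the documents allow in three ways:

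- **That a liver difference of the pilot's size would usually be missed because of the t-test.** The pilot reports no liver time contrast and no time to intervention. Where power is poor, the rank-sum test is also weak, so sample size is the main problem there.
- **That many contrasts are too small for a t-test.** The projection below 50 patients applies to liver time to intervention only. At the larger contrasts Student's test has about 79-100% power for the illustrative ratio.
- **That Aim 2 rests on this test.** The question of when to image has its own announced analysis, although its method is not given.

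It is also fair to say that the assumed spread drives the result. At log-SD 0.5 the loss is modest, and nothing in the documents excludes that value.

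What the reply does not remove is that the pooled test is the only method named, for outcomes whose recording rules give them a floor and, for transfusion, zeros, in groups of unequal size. Welch's test costs almost nothing when the variances are equal and protects the error rate in large samples when they are not.

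**Conclusion.** The point holds as a minor one. The plan should not rely on the pooled t-test alone for timing, stay and transfusion.

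The harm depends on spreads that the documents do not give. If both groups have the same shape, the 5% level is kept and the cost is power: large for liver time to intervention at log-SD 0.8-1.2, modest at 0.5, and small for most larger contrasts at the illustrative ratio. If the groups differ in spread, the error rate moves in either direction and stays off at any sample size. A reader might conclude that it is generally far from 5%. That needs an SD ratio near 2.7; at a ratio of 1.4 it is about 7% or 3%.

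These figures assume log-normal data and pilot proportions that carry over to the full study.

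**What to change.** Replace the single sentence on continuous variables with a rule in two parts:

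- **Mean differences (for example stay and transfusion):** Welch's t-test or a bootstrap confidence interval.
- **Timing of imaging and intervention:** report median and IQR, and compare by the Wilcoxon rank-sum test or by a linear mixed model on log time with a site random intercept. State that these compare distributions or geometric means, not arithmetic means.

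Add that liver time to intervention is expected to involve few patients and will be read mainly as description, since it stays underpowered with any test at the larger assumed spreads.

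The cost is a few lines of text and no new data. The real downside is the change of estimand for timing, so the target should be chosen and written down before the data are analysed.

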In this small pilot study we were unable to achieve all of our primary and secondary endpoints. Additionally, interventions in low grade injuries are uncommon, and a larger data set would allow for delineation in management between low, moderate and high grade splenic and hepatic injuries. This study did not have power due to a limited number of patients receiving interventions, thus making characterization of types of interventions and final outcomes difficult.

A large multicenter trial would allow for appropriate power for the study and thus allow for us to meet our endpoints. There are multiple variables affecting the management of blunt splenic and hepatic injuries and currently no clear guidelines exist in regards to repeat imaging. Gaining a better understanding of types of delayed complications, how they present, and current management strategies would assist in creating a standardized algorithm in the treatment of this patient population.

Specific Aims of Multicenter Study

Aim 1: To define which blunt splenic and hepatic injuries are at risk of delayed complications in order to develop a societal management guideline.

Aim 2: To ascertain which patients warrant repeat imaging and when this imaging should be performed.

Aim 3: To define what interventions are needed based upon delayed complications found radiographically.

Aim 4: To analyze 30 day readmission rates to the hospital due to spleen and/or liver injury.

Methods

This will be a retrospective observational study. Patients will be managed according to the surgeon's discretion. The study will enroll a total of 5,000 subjects at minimum. This study plans to enroll 200 patients at our institution, Penn Medicine Lancaster General Health. The number of subjects that will be enrolled at each additional participating site is 200.

Inclusion Criteria:

• All patients (all ages) who present with blunt trauma to the spleen and/ or liver

Exclusion Criteria:

- Patients who suffer a penetrating mechanism
- Patients transferred out to another facility prior to admission

Updated Terms/Definitions:

• **Clinical Change (CC) (to replace Physician Discretion)**- repeat imaging prompted by patient factors including vital sign changes, lab abnormalities, abdominal pain, and patient symptoms

• Non Clinical Change (NCC) (to replace Standard Protocol)- repeat imaging prompted by institutional protocol/ recommendations, individual physician practice pattern, or that performed on a scheduled basis

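### The planned mixed model has no safeguard if hospitals' complication risk is related to their share of protocol-driven scans, so the adjusted odds ratio for imaging reason may absorb between-hospital differences

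*Supplement*

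**What the plan says.** The adjusted analysis is set out in Data Collection and Statistical Analysis, in the same words in both copies of the protocol: "For multivariate analysis, a mixed effect multinomial logistic regression will be run", with delayed complication (yes or no) as the outcome. A second model of the same kind takes intervention as its outcome. The label multinomial does not fit a binary outcome; I read both as mixed-effects logistic regressions. Reporting is fixed by "Data will be reported as adjusted odds ratios with 95% confidence intervals" and "Statistical significance will be defined by a p<0.05".

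The target of 5,000 patients "is recommended to identify a significant difference between the non clinical change and clinical change group", so the NCC v CC contrast is the one the study is sized for.

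Updated Terms/Definitions describes NCC imaging as "repeat imaging prompted by institutional protocol/ recommendations, individual physician practice pattern, or that performed on a scheduled basis". Background & Significance adds: "Institutional variance exists in management of these injuries regarding serial laboratory values", and goes on to list follow-up imaging among the practices that vary.

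The plan does not name the random effect, list the fixed effects, or say that imaging reason is one of them. It has no fixed site effects, no split of the imaging effect into within-site and between-site parts, and no sensitivity analysis.

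**The concern.** A random intercept treats each site's baseline log-odds as independent of the covariates. If sites with more NCC imaging also have a higher or lower complication rate among scanned patients, the NCC coefficient becomes a weighted average of the within-hospital contrast and a between-hospital difference. The second part is not an effect of imaging reason.

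Three features of the protocol make such a link plausible:

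- NCC status depends partly on hospital policy, so the NCC share will very likely differ by site.
- The primary outcome is counted among scanned patients, and in the pilot only 45% of splenic and 33.4% of hepatic injuries were re-imaged. A hospital with a scanning protocol scans patients whom another hospital would never scan.
- The data dictionary records one reason, for the first repeat scan only. In the pilot, protocol imaging found splenic complications at 2.4 days v 4.4 days. A patient who would have deteriorated later can therefore be coded NCC at a protocol hospital and CC elsewhere.

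The study is meant to inform a management guideline. A difference between hospitals could be read there as a difference due to the reason for imaging.

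**Working it through.** **1. The plan's own figures.** For two proportions with pooled variance, two-sided 0.05, 80% power (not stated, but it reproduces the tables) and equal groups, n per group = [1.96·√(2p̄(1−p̄)) + 0.8416·√(p₁(1−p₁)+p₂(1−p₂))]² / (p₁−p₂)².

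- Spleen, 0.47 v 0.42: (1.3775 + 0.5908)² / 0.0025 = 1,549.6, rounded up to 1,550 per group, 3,100 in total.
- Liver, 0.20 v 0.27: (1.1753 + 0.5029)² / 0.0049 = 574.7, rounded up to 575 per group, 1,150 in total.

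The other four rows (8,614; 1,582; 2,256; 696) also reproduce. The formula contains no site term.

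**2. Layout taken from the documents.** 5,000 / 200 = 25 sites. Re-imaged spleens: 3,500 × 105/235 = 1,564, about 63 per site. Re-imaged livers: 1,500 × 122/365 = 501, about 20 per site. Pilot NCC share: 38/105 = 36% (spleen) and 50/122 = 41% (liver).

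**3. Two types of site (spleen).** 25 sites × 62 patients, true within-site odds ratio 1, half the sites protocol-driven, 250 runs per row. The difference in site log-odds and the NCC shares are assumptions. Entries are mean log OR / mean SE / false-positive rate.

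| Site log-odds difference; NCC shares | Random intercept only | Plus site NCC share |
|---|---|---|
| None | 0.004 / 0.118 / 6.4% | 0.004 / 0.126 / 4.0% |
| 0.5; 60% v 12% | 0.105 / 0.123 / 13.2% | −0.006 / 0.127 / 3.2% |
| 0.8; 60% v 12% | 0.118 / 0.127 / 18.0% | −0.007 / 0.128 / 3.2% |
| 0.5; 80% v 5% | 0.235 / 0.139 / 40.0% | −0.008 / 0.164 / 3.6% |

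Shares of 60% v 12% average 36%, as in the pilot. Shares of 80% v 5% average 42.5%, so the last row is an extreme case. The planned spleen effect is |ln 0.82| = 0.198, so a bias of 0.105 is about half of it and 0.235 exceeds it.

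These rows match a residual between-site SD of about 0.3. Repeats at that SD gave 12.3% and 12.5% for the second row, and 36.7% and 41% for the last. The result is sensitive to the SD, at shares of 60% v 12%:

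- SD 0: about 31% for differences of both 0.5 and 0.8.
- SD 0.5: log OR 0.059 and 0.084, false-positive rates 6.0% and 7.3%.
- SD 0.3 with a site difference of only 0.25: 6.7%.

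**4. Graded link, both organs.** 25 sites, true odds ratio 1, 1,000 runs per scenario. Assumed: site SD 0.3, 0.5 or 0.8; SD of the logit NCC share 1 or 2; correlation ρ between site risk and NCC share.

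| ρ | False-positive rate, random intercept | Mean OR |
|---|---|---|
| 0 | 4.2–6.0% | about 1.00 |
| 0.3 | 5.0–9.3% | 1.03–1.14 |
| 0.6 | 7.5–20.1% | 1.05–1.32 |
| 0.9 | 7.9–37.7% | up to 1.24 (spleen), 1.57 (liver) |

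With the site NCC proportion added, the rate is 3.5–6.4% and the mean OR 0.99–1.02 in all 48 scenarios. The bias takes the sign of the assumed link. In size it can match the planned effects (0.82, or 1/0.82 = 1.22, for spleen; 1.48 for liver).

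**The case against.** A reader might infer that NCC imaging is institution-driven by definition, and that the false-positive rate therefore does exceed 5%. The documents do not support that. NCC also covers individual physician habit and scheduled scans, which can vary within a hospital. The definition implies that NCC share differs by site. It does not imply that share is tied to underlying risk, and with no tie the error rate stays about nominal.

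Four further objections carry weight:

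- **The model is inferred.** The plan names neither a site random effect nor an imaging-reason term. Aim 1 asks which injuries are at risk, so the adjusted odds ratios could be meant for injury grade and similar factors. Against this, NCC v CC is the contrast the sample size serves, and site is the natural grouping for 25 hospitals.
- **The size is unstable.** With shares of 60% v 12%, moving the assumed residual site SD from 0 to 0.5 takes the false-positive rate from about 31% to 6–7%. No single figure should be quoted as the expected error.
- **Case-mix adjustment is left out.** The simulations have no patient covariates. Grade, ISS, AIS, TRISS and vital signs are collected; adjusting for them would remove some of the site difference, by an unknown amount.
- **The random intercept already helps.** In one strong-link spleen scenario (ρ 0.9, site SD 0.5, logit-share SD 2) the pooled chi-squared test rejects in 98.1% of runs and the random-intercept model in 32.1%.

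These points limit the claim to a conditional one. They do not supply the missing safeguard.

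**Conclusion.** The point stands in conditional form. Under the natural reading of the plan, the adjusted NCC v CC odds ratio is open to residual confounding by site, and nothing in the text would detect or remove it. If site risk is unrelated to NCC share, the false-positive rate is about 5% and no harm follows. With moderate links it is roughly 6 to 20%; with extreme shares, a very strong link or no other site variation it can reach 30 to 40%. All of this depends on the assumed site SD, site difference and NCC shares, and on how much case-mix adjustment absorbs. The documents establish neither the existence nor the direction of the link, only that it is plausible. Because the remedy needs no new data and restores a near-nominal error rate in every setting tried, it is worth making before analysis.

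**What to change.** In Data Collection and Statistical Analysis, for both the complication model and the intervention model:

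- call the model a mixed-effects logistic regression, name site as the random intercept and list the fixed effects;
- enter imaging reason as two terms: the patient's NCC/CC code and the site's proportion of NCC scans;
- report the patient-level term as the within-site odds ratio;
- add a logistic model conditional on site as a sensitivity check.

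Site identifiers are already assigned (Waiver of Consent and HIPAA), so the cost is wording and one derived covariate.

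Statistical costs:

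- The standard error rises by about 1–3% in the two 60% v 12% settings (0.127 to 0.128; 0.123 to 0.127). It rises by about 7% with no site difference (0.118 to 0.126) and about 18% with extreme shares (0.139 to 0.164).
- The conditional check learns nothing about imaging reason from sites whose scans are all NCC or all CC.
- The within-site odds ratio still carries patient-level confounding by indication, because CC patients are scanned on account of a clinical change. The report should say so.
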